#### **F.3.4. General Procedures**

##### ***F.3.4.1. Descriptive Statistics***

Dependent and independent variables in all models will be described using appropriate statistics which may include simple frequencies, mean, standard deviation, median, skewness, and kurtosis.

##### ***F.3.4.2. Bivariate Statistics***

The preceding subsections have largely dealt with multivariable regression models. As a preliminary step in modeling efforts, we will also investigate simple bivariate relationships between outcomes and explanatory variables of interest using appropriate bivariate statistics which may include but are not limited to t-tests, one-way analysis of variance, chi-squared or Fisher's exact tests.

##### ***F.3.4.3. Model Specification and Evaluation***

The preceding sections describe our general analytic approach. In practice, we aim to specify models that are appropriate to the demands of the data; therefore, we reserve the right to amend and/or alter our statistical methods and approach based model diagnostics and/or new techniques that come to our attention. Different models will also be explored to assess the robustness of our qualitative findings to alternative specifications.

##### ***F.3.4.4. Multiple Comparisons***

In the evaluation of secondary outcomes, we anticipate multiple comparisons within a family of outcomes where we consider families of outcomes to be groups of similar outcome measures within a domain (e.g.

resident education outcomes). To control for familywise error rate in conducting multiple hypothesis tests, we will adjust the overall study p-value ( $p=0.0444$ , see §F.4) using the Bonferroni correction.

#### **F.4. STATISTICAL SIGNIFICANCE LEVEL**

The overall level of statistical significance for this study will be set at  $p<0.05$ . One interim analysis is planned for the midpoint of this study. Assuming an O'Brien-Fleming alpha-spending function, the overall  $\alpha=0.05$  will be adjusted (LANDEMTS, Stata module) to  $\alpha_{\text{interim}}=0.0056$  for the interim analysis and  $\alpha_{\text{final}}=0.0444$  for the final analysis.

In analyses where there are multiple comparisons – for example, as in the case of multiple tests of a single hypothesis using different indicators for the same underlying construct in separate models, p-values will be adjusted using Bonferroni's method or another similar method to control for the family-wise error rate.

## **F.5. PLANNED INTERIM ANALYSIS**

### **F.5.1. Interim Analysis Overview**

A planned Interim Analysis will be undertaken at the midpoint of the Study Period. The purpose of the Interim Analysis is to assess whether there are any excess resident safety/wellness risks with respect to burnout that would raise ethical concerns about trial continuation.

The Interim Analysis will assess whether there are statistically significant differences in resident burnout scores across study arms (§F.3.1.2).

Results of the Interim Analysis will be reported to the DSMB (§D.12). Based on results of the Interim Analysis, the DSMB is charged with deciding whether the Trial should be terminated early or if the Trial can continue per protocol. Results of the Interim Analysis will not be used to modify Trial design or protocol.

### **F.5.2. Schedule of Interim Analysis**

The planned Interim Analysis is scheduled for April 2021. This is approximately midpoint through the SECOND Trial Study period, as the first SECOND Trial Resident Survey after dissemination of the Intervention will occur in January 2021.

ACS NSQIP data for the subset of SECOND sites that participate is scheduled to be delivered to the Study Team in January 2021. Because of ACS NSQIP data collection procedures which allow participating hospitals 120 days after the date of a procedure to complete data collection and entry.

A confidential Interim Report will be circulated to DSMB members in May 2021. A DSMB conference call is scheduled for May 2021.

### **F.5.3. Trial Stopping Rules**

The DSMB will review the results of the analysis and will decide whether any statistically significant differences in resident burnout scores across arms are clinically significant. The DSMB will have the responsibility to recommend trial continuation or early termination. Early termination will be based on two considerations: (1) finding statistically significant differences in burnout scores between Control and Intervention arms, and (2) DSMB finding the statistically significant differences *are also clinically significant* – i.e., that the magnitude of differences pose real welfare advantages/disadvantages to residents. If both of these conditions hold, and the DSMB votes to recommend early termination of the trial, then the trial will be terminated following the DSMB meeting to discuss the Interim Analysis.

### **F.5.4. Interim Analysis Statistical Methods**

We expect data for the Interim Analysis to come from the 2021 SECOND Trial Resident Survey. Resident burnout will be measured as previously described in §E.1. We will follow statistical methods that have already described for the analysis of resident burnout, which are outlined in §F.3.1. As discussed in §F.4., the level of statistical significance for the Interim Analysis will be set at  $p_{\text{Interim}} < 0.0056$  to maintain an overall significance level of  $p < 0.05$  for the SECOND Trial as a whole.

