## F.3. STATISTICAL EVALUATION PLAN

### F.3.1. Analysis of Primary Outcome

The primary study hypothesis is that:

- Residents in programs randomized to Intervention will have lower mean burnout scores compared to residents in programs randomized to Control

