#### F.3.1.2. Adjusted Analyses

Covariate adjustment in evaluations of randomized trials is generally done for purposes of increasing statistical efficiency by reducing variance within treatment groups. Covariate adjustment is also sometimes also undertaken on the basis of chance imbalance of baseline characteristics between study groups. Although programs will be randomized to treatment arms in this study, we anticipate considerable variation in the number of ABSITE respondents per program. In the 2019 ABSITE data, the average program had 23 resident respondents (mean=23.11, SD=11.15; coefficient of variation=48%), but the range spanned from a minimum of 3 residents per program to a maximum of 59 residents per program. Such dispersion in cluster sizes may lead to imbalance of resident characteristics

Thus, our analytic approach to evaluating our primary hypothesis will be to estimate a 2-level hierarchical linear model of the general form:

$$y_{ij} = \alpha_0 + \beta_0 TREAT_j + \beta_1 x_{1ij} + \beta_2 x_{2ij} + \cdots + \beta_k x_{kij} + \gamma_1 z_{1j} + \cdots + \gamma_m z_{mj} + \zeta_j + \epsilon_{ij}$$

where  $y_{ij}$  is the burnout T-score of resident  $i$  in program  $j$ ,  $TREAT_j$  is the study arm assignment of program  $j$ , and  $x_{1ij}$ - $x_{kij}$  are resident-level covariates and  $z_{1j}$ - $z_{mj}$  are program-level covariates to be adjusted for, including sampling stratification variables. In this model, under randomization of programs to study arms, the coefficient  $\beta_0$  is the adjusted population-averaged intent-to-treat estimate of the effect of assignment to intervention on mean resident burnout. A coefficient  $\beta_0 < 0$  that is statistically

significant with a one-tailed  $p<0.0443$  provides evidence supporting the effectiveness of the intervention over usual care. Other parameters in the model are the constant ( $\alpha_0$ ), coefficients on other resident-level covariates ( $\beta_1-\beta_k$ ), coefficients on program-level covariates ( $\gamma_1-\gamma_m$ ), program-level random intercepts ( $\zeta_j$ ) and individual-level errors ( $\epsilon_{ij}$ ).

Covariates may include variables listed in §E.3.: resident gender; resident relationship status; resident race; program type; program size; and randomization variables such as the quartile of program  $j$  ranked by 2019 program-level mean burnout scores. This list of covariates is subject to change.

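### The interim safety look is contradictory on direction: the stopping rule covers harm, but the test it cross-refers to recognises only lower burnout in Intervention, and 0.0056 has no stated tail

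*SAP*

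**What the plan says.** **Purpose.** SAP F.5.1 says the interim analysis is there to "assess whether there are any excess resident safety/wellness risks with respect to burnout that would raise ethical concerns about trial continuation".

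**Comparison and method.** F.5.1 goes on: "The Interim Analysis will assess whether there are statistically significant differences in resident burnout scores across study arms (§F.3.1.2"). F.5.4 adds: "We will follow statistical methods that have already described for the analysis of resident burnout, which are outlined in §F.3.1". F.5.4 and F.4 set the interim level at 0.0056 and give no tail.

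**The criterion referred to.** The hypothesis in F.3.1 is directional: "Residents in programs randomized to Intervention will have lower mean burnout scores compared to residents in programs randomized to Control". F.3.1.2 then describes a negative treatment coefficient that is "significant with a one-tailed" p below 0.0443, and says that such a result "provides evidence supporting the effectiveness of the intervention over usual care".

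**Stopping rule.** F.5.3 names two considerations. The first is "finding statistically significant differences in burnout scores between Control and Intervention arms". The second is that the DSMB also finds the differences clinically significant, meaning "that the magnitude of differences pose real welfare advantages/disadvantages to residents". Termination follows if both hold and the DSMB votes to recommend it.

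**The concern.** The purpose and the stopping rule treat the interim as a safety look that could go either way. The cross-references lead to a criterion that can be met only when burnout is lower in Intervention. If that criterion is applied at the interim, a rise in burnout in Intervention gives a one-tailed p near 1 and is reported as not significant, so consideration (1) of F.5.3 is not met. No section of the SAP states a harm boundary or a two-sided interim test.

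This is the only formal stopping rule and there is one interim look. D.12.2.5.1 schedules DSMB meetings in May 2021 and May 2023, the second after the final analysis. The direction of the test should be settled before unblinded interim results exist.

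**Working it through.** **1. The plan's interim level.** The O'Brien-Fleming-type spending function at half information, with a single alpha of 0.05, gives 2 × [1 − Φ(1.960/√0.5)] = 0.00557, which rounds to 0.0056. The remainder is 0.05 − 0.0056 = 0.0444. Both figures in F.4 reproduce. Spending 0.025 in each tail would give 0.00305 in total. The figure 0.0056 thus comes from spending one alpha of 0.05, which fits a one-sided 0.05 design but does not prove one.

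**2. The plan's detectable differences (Exhibit D.8.B).** The formula is MDD = (z_α + z_0.80) × SD × √[2(1 + (m − 1)ICC)/(km)], with SD 9.027, ICC 0.012 and alpha 0.0443. For k = 110 programs per arm and m = 20 residents:

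- Standard error: 9.027 × √(2 × 1.228/2200) = 0.3016.
- Two-sided: (2.011 + 0.842) × 0.3016 = 0.860; the exhibit states 0.86.
- One-sided: the same formula gives 0.767.

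All 12 rows match the two-sided calculation to within about 0.005. Power was therefore computed two-sided, F.3.1.2 tests one-tailed, and the interim level has no stated tail.

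**3. Standard error at the interim.** The inputs are 103 and 106 programs (Exhibit D.9), SD 9.027 and ICC 0.012 (Exhibit D.8.B). The assumption of 20 residents per program is close to the mean of 19.873 in D.8.1.

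SE = √[9.027² × (1 + 19 × 0.012)/20 × (1/103 + 1/106)] = 0.309.

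The difference detectable with 80% power at two-sided 0.0443 is 2.853 × 0.309 = 0.88 points.

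**4. Chance of flagging a true harm of +0.88 points.** Critical values for p < 0.0056 are 2.536 (one-sided) and 2.770 (two-sided).

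| Test at the interim | Probability of a flag |
|---|---|
| One-tailed for benefit, 0.0056 | Φ(−2.536 − 2.853) = about 4e-8 |
| Two-sided, 0.0056 | Φ(2.853 − 2.770) = 53% |
| One-sided for harm, 0.0056 | Φ(2.853 − 2.536) = 62% |

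For a true harm of +1.5 points these become essentially 0%, 98% and 99%.

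**5. Sensitivity to cluster size.** Step 4 does not change at 15 or 25 residents per program, but only because the harm is rescaled to the detectable difference each time. For a fixed harm of +1.0 point, with 104.5 programs per arm (209/2), the two-sided test flags it 54%, 68% and 78% of the time at 15, 20 and 25 residents. The one-tailed benefit test stays below 0.0000001 throughout.

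**6. The same data under the two readings.** With 20 residents per program, an observed difference of +1.0 gives a one-tailed p of 0.9994 and a two-sided p of 0.0012. One reading reports no significance; the other meets consideration (1).

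**The case against.** The strongest reply is that the plan does not bind the interim to the one-tailed test. The sentence in F.3.1.2 states when an effectiveness claim is supported, and it is tied to the final level of 0.0443. F.5.4 sets its own level without a tail. The methods it imports can be read as the hierarchical model alone; F.3.1.1 states no tail, and F.3.1.3 gives a directional hypothesis but no one-tailed test. F.5.1 and F.5.3 speak of differences, and of advantages as well as disadvantages. The power calculation is two-sided. All of this stands.

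A reader might therefore infer too much: that the stopping rule can never be triggered by harm. The documents do not support that, because a two-sided reading is open. The figure of 4e-8 does not support it either. Any one-tailed test behaves this way in its opposite tail, so the number shows what the disputed reading would cost and not which reading is meant. A reader might also infer that residents would be held in a harmful condition until 2023. The intervention is an offer that programs need not act on (D.1.2, D.5.4), and the DSMB reviews a full interim report and votes on its recommendation (D.12.2.4, D.12.2.5.3).

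The reply does not remove the contradiction. F.5.1 cites F.3.1.2 by number, and the only tail stated there is one-sided for benefit. An analyst could follow either route in good faith.

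**Conclusion.** The concern holds as an internal contradiction about direction. The interim is non-directional in its purpose and stopping rule, directional by cross-reference, and has no tail attached to its significance level. If the criterion of F.3.1.2 is carried over as referenced, higher burnout in Intervention cannot meet consideration (1). For a true harm of +0.88 points the chance of a flag is about 4e-8, against about 53% with a two-sided test at 0.0056.

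These figures rest on the plan's SD and ICC, on all 209 programs contributing, and on an assumed 20 residents per program. The contrast between the two readings holds across 15 to 25 residents.

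**What to change.** Reconcile F.3.1.2, F.4, F.5.1, F.5.3 and F.5.4:

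- **F.5.4:** state that the interim comparison is two-sided at p < 0.0056. Alternatively, state that a positive coefficient is tested at its own one-sided level, and give that level. A harm test supports no efficacy claim and so uses no efficacy alpha.
- **F.5.1 and F.5.4:** say that the interim uses the model of F.3.1.2 and that its one-tailed effectiveness criterion does not govern the interim.
- **F.5.3:** say that a significant difference in either direction meets consideration (1).
- **F.4:** state the sidedness of 0.05, 0.0056 and 0.0444.

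Either option in F.5.4 cures the defect. A more liberal harm level, such as one-sided 0.025, would be a preference beyond what the contradiction requires.

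The cost is wording only, with no new data. Under the two-sided option the benefit threshold at the interim becomes slightly stricter: 2.770 × 0.309 = 0.86 points instead of 2.536 × 0.309 = 0.78. With no true effect, the chance of a false harm flag is 0.28% under the two-sided test, or the stated level under a separate harm test. The DSMB can set such a flag aside under consideration (2).

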## **F.6. DATA MANAGEMENT AND ANALYSIS SOFTWARE**

Analytic software to be used in the SECOND Trial may include, but is not limited to:

- Stata MP Version 15
- SAS
- Microsoft Excel
- MPlus

## SECTION G

### LIMITATIONS

---

#### G.1. LIMITATIONS OF GENERAL STUDY DESIGN

- Participants in both Intervention and Control groups likely already have programs in place that address various aspects of resident wellbeing. As a pragmatic trial, we are not able or willing to request that participating programs deviate from what they have already implemented. Thus, the SECOND Trial intervention is properly seen as an offer of information (feedback reports and information on alternative interventions) on top of what may already be in place. Lack of a clean baseline and control group will attenuate any measurable effect of intervention towards zero.

#### G.2. LIMITATIONS OF SURVEY INSTRUMENTS AND ADMINISTRATION

- Data on mistreatment obtained through our survey instruments may be subject to a number of respondent biases that have been documented and discussed in various literature.
- In the past, our survey has been administered at the conclusion of the annual American Board of Surgery In-Training Examination (ABSITE), which is a 5-hour examination administered each January. Responses may be biased in either direction by either exam-related distress/fatigue or post-exam elation.
- Furthermore, various items in the survey have been administered in previous years. Thus, there is a chance that senior residents may have become sensitized to the survey instrument.

#### G.3. LIMITATIONS OF INTERVENTION

- Components of the intervention were developed by studying what selected programs had already implemented. Components that may have worked for a specific program may not be feasible and/or effective in another program due to differences in organizational and/or institutional environments.
- The intervention is only an offer of information – both information on a program’s own performance, as well as information on possible modes of action. However, no financial resources are given to programs to adopt and implement any action. Action may be differentially costly depending not only on the specific component to be implemented, but also depending on a program’s level of discretionary resources. Thus, failure to find any appreciable effect of randomization to intervention on resident burnout may not necessarily be due to the usefulness of the information itself, but due to insurmountable barriers to implementation.

#### G.4. LIMITATIONS OF STATISTICAL METHODS

- Our current implementation of item response theory (IRT) graded response model (GRM) does not account for the hierarchical nature of the ABSITE resident data, in which residents are

clustered within residency programs. In other words, IRT GRM parameters do not account for any clustering at the program level. Hierarchical IRT models have been developed, but are not readily implemented within IRT subroutines in standard software packages such as *Stata*. Hierarchical IRT models for ordered, polytomous variables are even less developed. We acknowledge our use of non-hierarchical IRT GRM in our current work. However, we note that our final models in which T-Scores are used as the outcome variable *do* account for the hierarchical nature of the data (§D.8). It is unclear what the implications are of ignoring program-specific effects in estimating the discrimination and location parameters in IRT GRM models. At this time, we surmise that finding a way to implement hierarchical IRT GRM models may entail greater costs than benefit.

- Given the large number of secondary outcomes, it may be unlikely that we will find any statistically significant effect of the intervention on secondary outcomes after controlling for familywise error rates.

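### F.3.4.4 fixes Bonferroni for the secondary families while F.4 leaves the method open; naming Holm's step-down in both would settle the choice and recover some power at the same familywise level

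*SAP*

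**What the plan says.** SAP F.3.4.4 (Multiple Comparisons) defines "families of outcomes to be groups of similar outcome measures within a domain". It then states the aim, "To control for familywise error rate in conducting multiple hypothesis tests", and names the tool: the study-level p of 0.0444 is corrected "using the Bonferroni correction". No alternative is offered there.

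SAP F.4 (Statistical Significance Level) covers several tests of one hypothesis that use different indicators of the same construct. There the rule is looser: "p-values will be adjusted using Bonferroni's method or another similar method to control for the family-wise error rate".

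SAP G.4 (Limitations of Statistical Methods) names no method. It notes the large number of secondary outcomes and says that, after familywise control, "it may be unlikely that we will find any statistically significant effect of the intervention on secondary outcomes".

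No secondary effect sizes, correlations or sidedness are given. The primary test in F.3.1.2 is declared "significant with a one-tailed" threshold, but nothing equivalent is said for the secondary tests.

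**The concern.** Two things are at issue.

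- **The method is not fixed.** A set of domain scores within one family fits both the F.3.4.4 description and the F.4 description. The first section prescribes Bonferroni and the second permits a substitute chosen later. F.3.4.3 also reserves a general right to change methods. On this wording, the procedure could be chosen once the p-values are known.
- **The named method gives away power.** Single-step Bonferroni is never more powerful than Holm at the same familywise level, and Holm needs no further assumption.

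At stake is how many of the learning-environment domains can be declared improved. Section B expects a measurable improvement in the learning environment, and Objective 3 sets out to refine the Toolkit. For both, which domains moved matters, and not only whether any did.

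**Working it through.** **Inputs from the SAP.** The familywise level is 0.0444 (F.3.4.4, F.4). The well-being family has m = 9: nine domains are listed in C.2.1 and F.3.2.1.A, and F.3.2.1.B says nine. The patient family has m = 18, the count of the list in C.2.3 and F.3.2.2.

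**Reproducing the plan's level.** F.4 spends an overall 0.05 with an O'Brien-Fleming-type function and "One interim analysis is planned for the midpoint of this study". At information fraction 0.5 the spend is 2[1 − Φ(1.960/√0.5)] = 0.00557, which rounds to 0.0056. The remainder is 0.05 − 0.00557 = 0.04443, which rounds to 0.0444. Both match F.4. D.8 and F.3.1.2 print 0.0443. The difference is immaterial here, since 0.0443/9 = 0.00492 and 0.0444/9 = 0.00493.

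**Thresholds.** Bonferroni compares every p-value with α/m. Holm orders the p-values, compares the j-th smallest with α/(m − j + 1), and stops at the first failure.

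- m = 9: Bonferroni uses 0.00493 throughout. Holm uses 0.00493, 0.00555, 0.00634, 0.00740, 0.00888, 0.0111, 0.0148, 0.0222, 0.0444.
- m = 18: Bonferroni uses 0.00247 throughout. Holm starts at 0.00247, then 0.00261, and ends at 0.0444.

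The first thresholds are equal and the later ones rise. So Holm rejects at least what Bonferroni rejects, and the two methods reject something in exactly the same data sets.

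**Assumptions for power (not in the SAP).** Two-sided tests; equicorrelated normal statistics with correlation 0.5; mean z of 2.85 for each real effect. Uncorrected power at 0.0444 is then Φ(2.85 − 2.010) = 80%. At the Bonferroni threshold for m = 9 it is Φ(2.85 − 2.811) = 52%.

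**Simulation, m = 9, 200,000 replicates:**

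| Real effects | Average power, Bonferroni | Average power, Holm | Gain (points) | P(at least one rejection), both | Familywise error, Bonferroni → Holm |
|---|---|---|---|---|---|
| 0 | – | – | – | 0.035 | 0.035 → 0.035 |
| 2 | 51.6% | 52.4% | about 1 | 0.695 | 0.029 → 0.033 |
| 4 | 51.6% | 54.2% | about 3 | 0.822 | 0.021 → 0.029 |
| 6 | 51.5% | 56.4% | about 5 | 0.873 | 0.014 → 0.026 |
| 9 | 51.5% | 62.3% | 10 to 11 | 0.909 | no true nulls |

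With all nine real, expected detections go from 9 × 0.515 = 4.6 to 9 × 0.623 = 5.6.

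**Sensitivity to correlation.** Over correlations from 0 to 0.8 the gain is 0.7 to 0.9 points with two real effects, 2.5 to 2.7 with four, 4.7 to 5.1 with six, and 9.7 to 11.4 with nine.

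**Patient family, m = 18, correlation 0.5.** Average power goes from 43% to 44% with four real effects, from 43% to 46% with nine, and from 43% to 53% with all eighteen.

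**The case against.** The strongest reply is that nothing here is an error. Bonferroni controls the familywise error for correlated outcomes and is merely conservative, F.4 already admits Holm, and naming any one method, Bonferroni included, would remove the inconsistency. That stands. This is lost efficiency plus an unsettled choice, not an invalid test.

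Four stronger readings are tempting and are not supported:

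- **That G.4 admits real effects will be hidden and Holm would cure it.** G.4 does not say that the effects are real. It speaks of finding any significant result, and the probability of at least one rejection is identical under both methods.
- **That 10 points is the expected gain.** It requires every domain to have a real effect. With two to six real effects the gain is about 1 to 5 points.
- **That correlation among the outcomes is the reason to switch.** Holm remains valid under correlation but does not exploit it. A resampling or joint-distribution method would be needed for that.
- **That the eighteen patient outcomes make the case larger.** Section B expects no negative effect on patient care, so assuming eighteen real effects contradicts the trial's own expectation.

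It is also fair to object that the family sizes are unsettled. F.3.2.1.A says seven domains and lists nine, E.2.1 has eleven rows, and the patient list has eighteen entries in C.2.3 but fourteen in E.2.3. Either procedure needs m fixed, so changing the method alone leaves that freedom in place.

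**Conclusion.** The point holds as a cheap improvement of low severity. F.3.4.4 and F.4 disagree on whether the method is fixed, and the method that is named can be replaced by one that never rejects less and keeps the familywise error at or below 0.0444 under any dependence. Realised familywise error does rise (for example from 0.014 to 0.026 with six of nine effects real) but stays within the limit.

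For the nine well-being domains the gain in average power runs from about 1 point to 10 or 11 points, depending mainly on how many effects are real. These sizes rest on assumed 80% uncorrected power per real effect, correlation 0.5 and two-sided tests, because the SAP supplies none of these. The ordering of the two methods and the equal chance of at least one rejection do not depend on those assumptions. The documents leave room for a late choice of method; they do not show that one is intended.

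**What to change.** Use the same sentence in F.3.4.4 and F.4: for claims of benefit, p-values within each listed family are adjusted by Holm's step-down procedure at the stated familywise level. Delete the open alternative in F.4. List the members of each family where the rule is stated, so that m is fixed before the data are seen.

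The cost is SAP wording only; no new data, model or assumption is needed. The drawback is that Holm has no simple matching simultaneous confidence intervals. Report unadjusted intervals, labelled as such, beside the Holm-adjusted p-values. The G.4 limitation should stay as written, because this change does not remove it.
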